5.7 Data Analysis

General. To enhance methodological rigor and to allow for accurate dissemination of our findings, we will follow CONSORT guidelines in the design, analysis, and reporting of this study.⁹⁵

Data Management. [name], with the assistance of [name], will supervise data management using the following services: Enrollment, randomization, tracking of interviews, and auditing of data. A single enrollment and randomization document will be developed to assign identification codes to participants during the pre-enrollment period to track their eligibility

status, and randomly assign participants. The PI and Co-Is will remain blind to the meaning of participant condition until unblinding, following data analysis. Similar to our prior studies, a tracking system will be developed to assist research personnel in managing follow-up interviews. This information will be covered during weekly staffing meetings involving Drs. [name], [name], and [name] as well as the research personnel. Data will be audited for: a) data quality control (% of scales returned for corrections after auditing); b) rate of data entry; and c) backlog of data that has not been entered. All scales will be audited for identifiers, item completeness, and consistency of major clinical indicators. We will store and manage data at the VA with access limited to pertinent study personnel. During the study, we will maintain a dialogue on the technical integrity of our procedures and on conceptual aspects of our project.

Randomization. Following consent, participants will be randomly assigned (1:1) to the CBT-TS or the educational control based on a concealed block randomization scheme. Block sizes will be four and overall, 50% of participants will be assigned to each condition.

Preliminary Analysis. For all variables, we will examine the distribution for potential nonnormality and outliers. If necessary, appropriate data transformations or alternative data analysis procedures (e.g., nonparametric, bootstrapping) will be used prior to data unblinding. Prior to outcome analyses, baseline demographic and outcome variables will be assessed for baseline equivalency. Categorical variables will be analyzed using chi-square tests; continuous variable differences will be assessed using pooled t-tests. Per missing data design (see **Missing Data**), if baseline differences are detected, these covariates will then be included in the final model as auxiliary variables to improve the plausibility of assuming data is MAR.⁹⁶

Primary Analyses in Support of the Specific Aims. **Aim 1 Hypothesis:** Participants receiving CBT-TS will be significantly more likely to initiate psychosocial pain treatment than participants in the control condition. Treatment initiation of psychosocial pain treatment will be treated as a binary outcome variable (0|1). A Cox Proportional Survival Analysis.⁹⁷ will be conducted to examine treatment initiation by the 6-month follow-up. This approach is like logistic regression except it accounts for missing data across the follow-up timepoints. Condition will be entered into the model as a predictor of whether a participant reported attending treatment by the 6-month follow-up. The assumption of proportionality will be tested in this model. A secondary logistic regression analysis will be conducted to examine treatment initiation by the end of the 6-month follow-up using worst case imputation of missing outcome to test robustness of any effects. Additional secondary analyses to demonstrate treatment robustness will be treatment initiation by the 1-month and 3-month follow-ups.

Aim 2 Hypothesis: Participants receiving CBT-TS will attend significantly more sessions of treatment during the 6-month follow-up period than participants in the control condition. The outcome will be sessions of psychosocial pain treatment attended during the 6-month follow-up period. Analyses will be conducted using MRM within a multilevel modeling (MLM) framework as this method allows for appropriate modeling of the covariance matrix when measures are repeated over time and can easily account for normal, skewed, and categorical data. MRM will be used, including treatment condition, follow-up time (centered on 6-month follow-up), and a condition by time interaction term as predictors of number of sessions of treatment attended.

Aim 3 Hypotheses: Participants receiving CBT-TS will have significantly (a) reduced pain severity and interference, (b) improved physical function, and (c) reduced opioid dose and risk

of misuse compared to participants in the control condition. The outcomes will be pain severity, pain interference, physical functioning, opioid dose, and risk of misuse. MRM will again be used. Treatment condition, follow-up time (centered on 6-month follow-up), and a condition by time interaction term will be included as predictors as will the relevant baseline autoregressors. Additional secondary analysis to demonstrate treatment robustness will involve centering time at the 1-month and 6-month follow-ups, allowing for examination of treatment differences at these timepoints.

Exploratory Analyses: Explore the effect of CBT-TS in increasing the initiation of and retention to other non-pharmacological pain treatments among Veterans receiving opioid analgesics for chronic pain. For treatment initiation and treatment retention, we will employ the same approach as described in Aims 1 and 2. As an additional set of exploratory analyses and consistent with an experimental therapeutics approach, we will explore beliefs as potential mediators of treatment initiation. Structural equation modeling (SEM) will be used to conduct these analyses. Latent variables (BHS, PTWS, PSEQ, PCS, TSK, MBQ, BQ) will be constructed to capture beliefs about opioids, treatment, beliefs that pain can be reduced, and hope. These variables will be included as potential mediators between condition and treatment initiation by month 6 as well as pain and opioid clinical outcomes at month 6. Prior to testing the mediation model, the direct effects of condition on treatment initiation, pain, and opioid outcomes at month 6 will be examined in one model. Next, the latent belief factors at month 3 will be included as mediators. All models will be conducted including relevant baseline autoregressors. Measurement invariance across conditions and across treatment initiation status will be established for the month 3 latent belief factors. All models will be re-analyzed using manifest variables instead of latent variables to test for model robustness. Any differences will be discussed. We will also explore variables such as gender, baseline dose, age, race/ethnicity, parent station type (1a-c, 2, 3) as potential moderators of treatment effect to drive further study.

Analysis in Support of Specific Aims for Optional Add-on Study: **Aim 1 Hypothesis:** African American participants receiving CBT-TS will be significantly more likely to initiate psychosocial pain treatment than African American participants in the control condition, compared to rates of treatment initiation in the rest of the sample. Treatment initiation of psychosocial pain treatment will be treated as a binary outcome variable (0|1). A Cox Proportional Survival Analysis⁹⁷ will be conducted to examine treatment initiation by the 6-month follow-up. Race will be dummy coded (0 = African American, 1 = other) and included as an independent variable as well as moderator of treatment condition.

Aim 2 Hypothesis: Treatment initiation for African American participants receiving CBT will be moderated by CBT treatment components, including individualization, non-judgment, self-expert, collaboration, and empowerment. We will restrict these analyses to African American participants and will include treatment condition, CBT treatment components, and condition by components interaction terms.

Exploratory: Explore the effect of race-related stress on treatment initiation and retention to other non-pharmacological pain treatments among African American Veterans receiving opioid analgesics for chronic pain. African Americans participants who experience higher levels/more

race-related stress will be significantly less likely to initiate or complete other non-pharmacological pain treatments for chronic pain.

Missing Data. An intent-to-treat (ITT) approach will be used, including all participants randomized to a treatment condition. Missing data in the full analysis set will occur if participants discontinue prior to the end of the study or do not complete an outcome measure. Participants will not be discontinued from the study because of non-adherence and all will remain in the study unless consent is withdrawn or if there are concerns regarding participant safety. Missing data for the ITT analysis set will be addressed using robust full information maximum likelihood (FIML), which is superior to most alternative missing data approaches even when data is missing completely at random (MCAR) or missing at random (MAR).^{96,98} Although the use of FIML will result in the least biased parameters, regardless of data missingness, several approaches will be undertaken to better understand the exact mechanisms for missing data. Little's MCAR test will be applied to all final models to determine whether data can be considered MCAR. Further, the results of analyses using study completers will be compared with results using the ITT approach to test sensitivity of study conclusions to study discontinuations. Baseline differences also will be explored between treatment completers and those that discontinue across study and demographic variables. If baseline differences are detected, these covariates will then be included in the final model as auxiliary variables to improve the plausibility of assuming data is MAR.⁹⁶

Power Analysis and Sample Size. A balanced randomization scheme (1:1) will be used for this trial. Power to detect the primary effects of interest for the Aim 1 Hypothesis involve testing whether CBT-TS, compared to the education control condition, increases treatment initiation of psychosocial pain treatment. Power to detect the primary effects of interest for the Aim 2 Hypothesis involve testing whether CBT-TS, compared to the education control condition, increases treatment retention. Power to detect the primary effects of interest for the Aim 3 Hypothesis involve testing whether CBT-TS, compared to the education control conditions, improves pain and opioid outcomes. Sample size was determined using Monte Carlo simulation studies (with 10,000 replications). For each of the hypotheses, it was determined that with a sample size of $N = 250$ we would have at least 80% power with an $\alpha = 0.05$ to find small effects of condition on treatment initiation and small-to-moderate effects on all other direct effects. This includes adequate power to detect all significant indirect effects. To adjust for potential attrition, the sample size was increased by 20%, resulting in a final sample of $N = 300$. Power analyses for the mediation models ($\alpha = .05$, $1 - \beta = .80$) indicates that with 300 participants we will be adequately powered to find mediation in the presence of small-to-medium paths from condition to the potential mediators and from the potential mediators to the primary (treatment initiation) and two secondary outcomes (pain and opioid clinical outcomes).

Type 1 Error Protection. To help control for Type 1 error, the Benjamini-Hochberg method will be used to adjust for the multiple comparisons proposed in the current study.⁹⁹ This method adjusts for multiple comparisons by controlling false discovery rate instead of family-wise error rate. It is less conservative than the more traditional Bonferroni methods, yet still provides adequate protection against Type 1 error and is the optimal solution to the multiple comparison problem in most practical situations.

Data storage, security, and confidentiality

Several procedures for protecting participant confidentiality will be implemented to reduce the risk of revealing participant identity. All informed consent forms will contain identifying information. To ensure confidentiality, each consent form will be labeled with a numeric identifier and will be stored in a double-locked file. These will be stored in separate double-locked files from other study materials. As noted in the Data Transport Memorandum, locked courier bags will be used to transport any sensitive study information (e.g., consents) outside VA.

The VA Informatics and Computing Infrastructure (VINCI) will be used for the storage of study data. VINCI is a major informatics initiative of the Department of Veterans Affairs (VA) that provides a secure, central analytic platform for performing research and supporting clinical operations activities. It is a partnership between the VA Office of Information Technology (OI&T) and the Veterans Health Administration Office of Research and Development (VHA ORD). VINCI includes a cluster of servers for securely hosting suites of databases integrated from select national VA data sources. VINCI servers for data, applications, and virtual sessions are physically located at the VA Austin Information Technology Center (AIRC), located in Austin, Texas. This secure enclave with 105 high-performance servers and 1.5 petabytes of high-speed data storage has multiple layers of security and disaster recovery to prevent data loss.

Study data will be kept in accordance with the Department of Veterans Affairs Record Control Schedule 10-1 (RCS 10-1). Storage and transfer of any Personally Identifiable Information (PII) or Protected Health Information (PHI) must be done in accordance with applicable VA and VHA policies and directives, state and federal regulations, and applicable statutes including the Health Insurance Portability and Accountability Act (HIPAA). Unless explicitly requested and approved by data stewards, all sensitive patient data must remain on VINCI project servers and only aggregate data without PII / PHI may be transferred from VINCI.

Prior to being uploaded to VINCI for analysis, data will be stored on a secure VA server to which only IRB approved VA research personnel have access. Should any identifiable information need to be shared between research team members, we will utilize a secure, SharePoint site or electronic communication with PKI encryption. Any identifiable paper data will be stored in two separate locked file cabinets (one for informed consents and the other for paper questionnaire data) in the offices of the Center for Excellence for Suicide Prevention at the Canandaigua VAMC a. After a participant completes the study, any identifiers will be removed from the paper questionnaire data immediately. Data analysis will occur in the VINCI framework.

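### Tests of baseline differences between randomised arms choose which variables join the final model, while Aims 1 and 2 pre-specify no baseline covariate

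*Combined protocol and SAP*

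**What the plan says.** Section 5.7, Preliminary Analysis: "Prior to outcome analyses, baseline demographic and outcome variables will be assessed for baseline equivalency", using chi-square tests for categorical and pooled t-tests for continuous variables. The consequence is that "if baseline differences are detected, these covariates will then be included in the final model as auxiliary variables". The stated reason is to make the MAR assumption more plausible. No significance level for a detected difference is given.

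Section 5.7, Missing Data, uses a similar sentence for a different comparison: participants who complete against those who discontinue.

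The models in the same section differ in what they pre-specify:

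- Aim 1 (Cox): condition only.
- Aim 2 (repeated-measures model): condition, time and their interaction.
- Aim 3: the same terms as Aim 2, and these "will be included as predictors as will the relevant baseline autoregressors". The exploratory mediation models also carry baseline values.

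Randomisation is 1:1 in blocks of four. No stratification factor is stated, so there is none to adjust for by default.

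**The concern.** Under proper randomisation the null hypothesis of each between-arm baseline test is known to be true. A small p-value marks a chance imbalance. It says nothing about whether the variable predicts initiation, attendance or dropout. The rule can therefore bring in irrelevant variables and will usually leave out useful ones.

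The word auxiliary can be read in two ways, and the plan does not choose:

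- If flagged variables become predictors beside condition, chance picks the adjustment set, and with it the hazard ratio being estimated.
- If they only support the full-information likelihood (FIML), the Aim 1 and Aim 2 effects are wholly unadjusted. How auxiliary variables would work in a Cox model is also not explained.

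At stake are the predictability of the primary model and whatever power baseline data could add. Some plausible predictors may never be tested: the rule covers demographic and outcome variables, whereas treatment willingness (PTWS) is listed in Table 4 as a belief.

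**Working it through.** **The plan's own figure.** 250 × 1.20 = 300 reproduces the final sample size. The claim of at least 80% power at 250 cannot be reproduced, because the effects appear only in words ("small effects of condition on treatment initiation and small-to-moderate effects on all other direct effects"). The power figures below therefore use assumed scenarios.

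**How often chance triggers the rule.** Section 5.5 lists 8 demographic variables and 3 examples of military background. Aim 3 lists 5 outcomes. That makes 16 variables. Assume a 0.05 level (not in the plan) and independent tests:

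- P(at least one flag) = 1 − 0.95^k.
- k = 16: 1 − 0.95^16 = 0.56, with 16 × 0.05 = 0.8 flags expected.
- k = 11: 0.43. k = 30 (roughly the whole baseline battery): 0.79.

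**What this does to Aim 1.** Simulated Cox trials used N = 300, blocks of four, censoring at 6 months and 16 independent baseline variables, of which one was prognostic. There were 1,500 trials per row. Control initiation, treatment hazard ratio (HR) and covariate strength are all assumptions. Log HRs of 0.3, 0.6 and 0.9 per SD are HRs of 1.35, 1.82 and 2.46.

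| Control initiation, treatment HR | Covariate log HR per SD | Unadjusted | Test-then-include | Pre-specified | Pre-specified minus rule |
|---|---|---|---|---|---|
| 10%, 2.2 | 0.3 | 71.9% | 71.5% | 71.7% | 0.2 |
| 10%, 2.2 | 0.6 | 69.1% | 68.5% | 72.5% | 4.0 |
| 10%, 2.2 | 0.9 | 64.5% | 64.2% | 72.6% | 8.4 |
| 20%, 1.8 | 0.3 | 72.0% | 71.5% | 72.4% | 0.9 |
| 20%, 1.8 | 0.6 | 67.2% | 66.6% | 71.3% | 4.7 |
| 20%, 1.8 | 0.9 | 61.1% | 60.9% | 71.3% | 10.4 |
| 30%, 1.65 | 0.3 | 74.0% | 73.3% | 74.5% | 1.2 |
| 30%, 1.65 | 0.6 | 67.4% | 67.7% | 74.3% | 6.6 |
| 30%, 1.65 | 0.9 | 60.1% | 60.5% | 72.5% | 12.0 |

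The simulation error of one power figure is about √(0.7 × 0.3 / 1,500) = 1.2 points. All three analyses were run on the same trials. At least one variable was flagged in 53% to 57% of trials, and the prognostic one in 4.4% to 5.9%. Test-then-include therefore has almost the same power as no adjustment.

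**Type I error.** With no treatment effect, 20% initiation and 3,000 trials per scenario, rejection rates were 4.2% to 5.4% across the three approaches.

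**Change of estimand.** In the 20%, log HR 0.9 row, the mean log HR for treatment was 0.527 unadjusted (HR 1.69) and 0.592 adjusted (HR 1.81). The true conditional value was 1.8.

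**Aim 2, rough guide on a linear scale.** Starting from 80% power, a baseline covariate with correlation r to the outcome gives power = Φ[(1.960 + 0.842)/√(1 − r²) − 1.960]. The result is 82% for r = 0.2, 84% for 0.3, 86% for 0.4 and 90% for 0.5. Session counts are likely to be skewed, so this is only indicative.

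**The case against.** The strongest reply is that nothing invalid happens. The unadjusted randomised comparison is sound, type I error is nominal, and covariate adjustment is a matter of efficiency. With weak predictors the gain is about nil, and the documents give no predictor strengths. Adjustment also makes the hazard ratio conditional. All of this stands. It limits the size of the point but does not rescue a rule that fails its own MAR purpose.

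Four stronger readings are tempting but not supported:

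- *That the covariates are picked after seeing results.* The rule is written in advance and applied before outcome analyses. Section 5.7 keeps the principal investigator and co-investigators blind to the meaning of condition until after data analysis.
- *That the Missing Data section has the same fault and should go too.* It compares completers with discontinuers, which does bear on missingness.
- *That a chance flag is close to certain.* The 79% figure needs about 30 tested variables, but the plan limits testing to demographic and outcome variables.
- *That Aim 1 is the endpoint with least power to spare.* No numeric effect size or event rate is given, so this cannot be shown.

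One may also doubt that prior treatment use is informative, since recent users are excluded. That exclusion covers only the past month (section 5.4), and one session counts as initiation (section 5.5), so earlier users can be initiators. How strongly prior use predicts initiation is unknown.

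**Conclusion.** The point holds for Aims 1 and 2. Between-arm significance tests are the wrong way to choose variables for the final model, whichever meaning of auxiliary is intended. It does not extend to Aim 3, where baseline values are pre-specified.

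The chance of at least one spurious flag is about 56% for 16 variables, assuming a 0.05 level and independence. A useful predictor is caught only about one time in twenty. The Aim 1 power forgone runs from about nil to about 12 points, entirely on assumed predictor strengths, initiation rates and hazard ratios. This is a loss of efficiency and predictability, not a threat to validity. It deserves correction because the remedy is cheap.

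**What to change.** 1. In Preliminary Analysis, remove the between-arm tests as a rule for selecting variables. The baseline comparison can remain descriptive.
2. Before unblinding, name a short covariate list for the Aim 1 Cox model and the Aim 2 model: baseline PTWS willingness for CBT-CP, ACT and MBSR; baseline opioid dose (MEDD); and prior psychosocial pain treatment from the medical record or Corporate Data Warehouse, with a stated look-back.
3. Keep the baseline values in Aim 3.
4. In Missing Data, keep the completer-versus-discontinuer comparison. Pre-list candidate auxiliary variables, chosen for expected association with dropout or outcome, and state that they are separate from the adjustment covariates.
5. Report the unadjusted Aim 1 and Aim 2 results as sensitivity analyses, and label the adjusted hazard ratio as conditional on the covariates.

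The cost is mainly plan wording. Section 5.5 has the modified PTWS covering all three therapies, records opioid dose, and describes warehouse data going back to 1979. The look-back of the baseline utilisation form is not stated in section 5.5, so it must be defined. The statistical price is a few degrees of freedom and a conditional rather than marginal hazard ratio.

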Methodology: Participants (N = 300) will be randomized to either the CBT-TS condition or an education control condition. Participants in both conditions will complete assessments on pain, treatment engagement, and opioid use at baseline, and 1-, 3-, and 6-months post-treatments to assess primary, secondary, and exploratory outcomes. Treatment initiation and retention will be assessed primarily through data extraction and chart reviews. Participants will include men and women Veterans who: (a) are English-speaking, (b) are 18 years of age or older, (c) are taking at least 20 mg morphine equivalent daily dose of opioid analgesics per day for ≥ 90 days, (d) have pain that occurs on at least half the days for 6 months or more, and score ≥ 4 on each of the three items of the PEG. Veterans will be excluded on the basis of: (a) having used a nonpharmacological approach to pain management in the last 30 days, (b) having cognitive impairment, and (c) being in hospice, undergoing oncology treatment, or having a recent or upcoming surgery

Data Safety Monitoring Plan: To ensure safety of participants in the study proposed and validity and integrity of data collected, the PI ([name]) will oversee all data and safety monitoring functions and the research team will be advised that he will be the primary contact overseeing these activities. The investigators will meet regularly to monitor study progress and discuss the implementation of monitoring procedures. He will also meet regularly with the research coordinator and staff to review monitoring procedures and ensure all efforts are being taken to minimize risks to participants. A Data Safety & Monitoring Board was not required by VA HSR&D.

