Assessments and Intervention: Veterans who are eligible and agree to participate will go through the informed consent process with research staff. Those who agree to participate will be asked to schedule a time to complete a baseline assessment and randomized to the CBT-TS condition or control. Following the baseline assessment, participants will then be scheduled a convenient time to conduct their intervention session (lasting approximately 45 minutes for both the experimental and the control condition). All study activities will be conducted by telehealth. Follow-up assessment will occur 1-, 3-, and 6-months post-treatment. At the conclusion of the 6-month follow-up assessment, participants will complete an exit interview describing their experiences with the study. Participants will receive compensation for their participation in the study. The compensation amount will be based on the following:

Baseline Assessment	\$50
1-Month Post-Treatment Follow-Up Assessment	\$40
3-Month Post-Treatment Follow-Up Assessment	\$40
6-Month Post-Treatment Follow-Up Assessment	\$40

Therefore, the total compensation for completing all the study components would be \$170. Payments will be made via direct deposit, check, or debit card following each study procedure listed above. Participants who do not complete the entire study for any reason will receive compensation for the components that were completed per the above schedule of payments.

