5.5 Study Evaluations

Medical Record Review and Treatment Utilization Form (TUF). Treatment utilization will be assessed through medical record review. The measure can be found in the **Appendix**. CAPRI and Joint Longitudinal Viewer will be used to access medical records. These are used at every VAMC and regional office and are accessible from every VA site of care. We will abstract data related to treatment utilization and medications across VHA facilities, including types of service (e.g., CBT-CP, chiropractic care), dates of service, number of sessions, and type and dose of medications. Non-VA medications known to VA providers and non-VA treatment notes are also included in the medical record. This data will be abstracted as available. Treatment initiation of psychosocial pain treatment is defined as attending at least one session of CBT-CP, ACT, or MBSR. We will also utilize data extraction from the Corporate Data Warehouse (CDW) to initially capture treatment utilization from medical records to assist in the medical record review. CDW contains financial, enrollment, demographic, diagnostic, treatment utilization, and other data across Veterans from 1979 to present. For training of the medical record chart review, the research staff will code 12 charts unrelated to the study and then meet to discuss and resolve differences. During the review for the study, they will overlap on 10 charts to facilitate agreement and ongoing discussion of differences will be addressed as needed. Drs. [name] and [name] will make the final decisions.

We will also collect self-report data on non-VHA care not identified in the medical record. *Self-report data will be exploratory* to evaluate the extent to which treatment was utilized outside the VHA and will not be included in the analyses of the primary and secondary outcomes. Participants will be asked at baseline and each follow-up period whether they have initiated treatments and the number of sessions for each type of treatment they have attended since the previous assessment. We will ask participants to provide information about where the treatment was received, and type of treatment (e.g., CBT-CP, MBSR, chiropractic, acupuncture).

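### The Aim 1 primary analysis is worded on reported attendance and visit-based missing data, contradicting the chart-based endpoint, and leaves no defined window for randomised participants who never have the session

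*Combined protocol and SAP*

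**What the plan says.** **Where the outcome comes from.** The abstract (Methodology) says: "Treatment initiation and retention will be assessed primarily through data extraction and chart reviews". Section 5.5 (Medical Record Review and Treatment Utilization Form) defines initiation as one or more sessions of CBT-CP, ACT or MBSR. It takes utilisation from the medical record, assisted by Corporate Data Warehouse extracts, and the abstracted items include service dates. Participants are also asked at baseline and each follow-up whether they have started treatment, but that information is labelled exploratory and "will not be included in the analyses of the primary and secondary outcomes".

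**How it is analysed.** Section 5.7 (Aim 1), repeated in the abstract (Data Analysis), says: "Condition will be entered into the model as a predictor of whether a participant reported attending treatment by the 6-month follow-up". Section 5.7 calls the outcome binary and prefers Cox to logistic regression because "it accounts for missing data across the follow-up timepoints". A secondary logistic regression is run "using worst case imputation of missing outcome to test robustness of any effects". The Missing Data paragraph counts data as missing when a participant leaves early or does not complete a measure.

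**The clock.** Section 5.7 (Randomization): "Following consent, participants will be randomly assigned (1:1) to the CBT-TS or the educational control". Section 5.1 books the intervention session after the baseline assessment, at a time that suits the participant, and then: "Follow-up assessment will occur 1-, 3-, and 6-months post-treatment". The Missing Data paragraph states: "An intent-to-treat (ITT) approach will be used, including all participants randomized to a treatment condition".

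No section gives the Cox time origin, the event date, the censoring rule, or the chart window for a randomised participant who never has the session.

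**The concern.** The sections describe different variables. Section 5.5 yields a dated, chart-based event that needs no contact with the participant. Section 5.7 describes a reported event whose absence is tied to follow-up timepoints. The reported variable will exist, because participants are asked for it at each follow-up, so an analyst who follows section 5.7 to the letter would use the variable that section 5.5 excludes.

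The missing-data rules have the same fault. A missed call does not make a chart outcome missing, yet the stated reason for Cox and the worst-case imputation both assume that it can. Nothing says that abstraction continues after missed visits.

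The window is also unanchored. It ends at the 6-month follow-up, which is counted from treatment, while randomisation comes earlier. A participant who never has the session has no 6-month date, and a first pain-treatment session between randomisation and the study session belongs to no stated period.

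At stake are events and power in the primary comparison and, if contact is lost differently by arm and outcome, the hazard ratio itself. The wording carries over: section 5.7 applies the same approach to the exploratory aim and repeats the Cox plan for the add-on study.

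**Working it through.** **1. The plan's own figure.** Section 5.7 (Power Analysis) sizes the trial at N = 250 and adds 20% for attrition: 250 × 1.20 = 300. The allowance is 50/300 = 16.7% of those randomised, and it covers every hypothesis, including initiation. The stated 80% power cannot be reproduced because no initiation rates or hazard ratio are given. All rates below are therefore assumptions.

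**2. What the allowance is worth if charts are read for everyone.** With control and CBT-TS initiation p₀ and p₁, n per arm and two-sided α = 0.05:
- events D = n(p₀ + p₁)
- HR = ln(1 − p₁)/ln(1 − p₀)
- power = Φ(½√D · ln HR − 1.96) (Schoenfeld)

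For 10% versus 20%, HR = ln 0.80/ln 0.90 = 2.12. With n = 150, D = 45 and power = Φ(2.52 − 1.96) = 71%. With n = 125, D = 37.5 and power = Φ(2.30 − 1.96) = 63%.

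| Assumed rates | HR | Events, 300 vs 250 analysed | Power, 300 vs 250 analysed |
|---|---|---|---|
| 10% vs 20% | 2.12 | 45 vs 37.5 | 71% vs 63% |
| 10% vs 22.6% | 2.43 | 49 vs 41 | 87% vs 81% |
| 15% vs 30% | 2.19 | 67.5 vs 56 | 90% vs 84% |

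(22.6% is the prior-use figure for another cohort in section 2.0, used here only as one point in a range.) One sixth of events and 6 to 8 points of power are at stake.

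**3. Simulation of the two readings.** Set-up: 150 per arm, constant hazards, 6 months, 1,000 replicates, Cox model with a two-sided 5% test. The chart reading uses service dates for all 300. The visit reading dates an event to the next scheduled visit and censors dropouts at their last visit, which is baseline, month 1 or month 3 with equal chance.

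| Truth and visit dropout | Chart: HR, events, rejection | Visit: HR, events, rejection |
|---|---|---|
| 10% vs 20%; 20% dropout, unrelated to outcome | 2.12, 45, 67% | 2.08, 38, 57% |
| 15% both arms; 20% dropout, unrelated to outcome | 1.01, 45, 4% | 1.01, 38, 4% |
| 15% both arms; dropout 5% in CBT-TS initiators, 40% in control initiators, 20% in others | 1.00, 45, 5% | 1.35, 37, 13% |
| 10% vs 20%; same related dropout | 2.10, 45.5, 68% | 2.79, 40, 87% |

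Hand check of the event loss in the first row: dropouts lose about 1, 5/6 or 1/2 of their events according to last visit, a mean of 0.778. Then 0.20 × 0.778 = 15.6%, and 45 × (1 − 0.156) = 38.0, which agrees with the simulated 38. About 300 × 0.20 × 1/3 = 20 participants contribute no follow-up at all.

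**4. The secondary logistic check only.** Worst case is not defined. With 10% versus 20% and 20% of outcomes called missing, setting all missing to not initiated gives 0.8 × 10% = 8% versus 0.8 × 20% = 16%, so the difference falls from 10 to 8 points. Setting missing controls to initiated gives 8% + 20% = 28% versus 16%, a reversal. This does not touch the Cox model, but it shows why chart-observable outcomes should not enter the imputation.

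**The case against.** A reader might infer more than the documents say. These are the stronger readings, and why each fails:

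- **The primary analysis uses self-report.** This rests on one verb. Section 5.5 is the specific rule on sources and excludes self-report, and the abstract agrees that charts are the main source. The text is a contradiction to reconcile, not evidence of what will be done.
- **Known outcomes will be thrown away.** No sentence says that a missed call censors anyone. The Missing Data paragraph also serves the questionnaire outcomes, and the Treatment Utilization Form at follow-up in Table 4 is a record review that need not involve contact. The plan permits the loss but does not require it.
- **Intent-to-treat is broken.** The plan includes everyone randomised and does not discontinue anyone for non-adherence. The post-treatment timing describes assessments and is not stated as the Cox origin. What stands is that the window closes at one of those assessments and is undefined for those who never have the session.
- **The hazard ratio is biased.** With unrelated dropout it hardly moved. Bias appeared only under a strong pattern (5% versus 40% dropout among initiators) that nothing in the documents supports.
- **Charts cover everyone.** Non-VA care is abstracted only where available, and withdrawal of consent may end access. Some outcomes can be truly missing, so a missing-data rule is needed; it should be tied to charts and not to visits.

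**Conclusion.** Wrong as written. Section 5.7 and the abstract's analysis paragraph contradict the chart-based definition in section 5.5 and the abstract's own methodology. The origin, event time and censoring rule of the primary survival analysis are not stated, and randomised participants who never have the session have no defined window. This is more than missing detail, because following section 5.7 literally would use the excluded variable and could treat chart-observable outcomes as missing.

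The dependable cost of the visit-based reading is precision: about one sixth of events and about 10 points of power (67% to 57%) at an assumed 10% versus 20% initiation with 20% unrelated visit dropout. Bias is conditional on dropout that depends on both arm and initiation; under the assumed pattern a null effect showed as a hazard ratio of 1.35 with 13% rejection. These sizes rest on assumed rates and dropout. The contradiction and the undefined window do not.

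**What to change.** Rewrite Aim 1 in section 5.7 and in the abstract so that:

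1. The event is the first chart-documented session of CBT-CP, ACT or MBSR, replacing the wording about reported attendance.
2. The event time is the service date.
3. Time zero is the randomisation date, with one fixed window of the same length for all randomised participants.
4. Charts are abstracted whether or not the session took place or the follow-up calls were completed.
5. Censoring occurs only at death, withdrawal of permission for chart use, or the end of the window.
6. Worst-case imputation is defined by arm and limited to participants whose charts cannot be obtained.

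Carry the same wording into the 1- and 3-month analyses, the exploratory aim and the add-on study. Keep visit-based windows for the questionnaires.

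The cost is wording, settled before unblinding; the charts and dates are already to be collected. There are two limits. The window will include the short time between randomisation and the session, and non-VA care will still be captured only where it reaches the record. Moving randomisation to after the baseline assessment is not needed for this fix.
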